3.6.3 Study day

For the study day calculation, if the event or assessment date is after the randomization date or after the treatment start date, the following calculations listed below apply:

The study day *for safety assessments* (e.g. adverse event [AE] onset, laboratory abnormality occurrence, vital sign measurement, dose interruption etc.) will be calculated as:

The date of the assessment / event - start date of study treatment + 1 day.

If an AE starts before the start of study treatment the study day displayed on the listing will be negative. In this case the study day will be calculated as:

The date of onset of the event - start date of study treatment.

The study day *for efficacy assessments* (e.g., efficacy endpoints EFS and OS, response assessment, quality of life [QoL] etc.) will be calculated as:

The date of the assessment / event - randomization date + 1 day.

For any assessment or events that happened **prior to the start of the study drug or randomization**, e.g., time since diagnosis of disease, the study days will be calculated for safety assessments as:

Study Day = Event date - Date of first study treatment.

Note that the day of first dose of study treatment is Day 1 and the day before the date of first study treatment is Day – 1, not Day 0.

In this study, ‘death’ is an efficacy endpoint. However, it will also be included in safety analysis. For safety, the ‘study day’ will be calculated following the rules for safety assessments as described above. For efficacy ‘time-to-event’ variables, the study day will be derived following the rules for non-safety assessments as described above. The study day will be displayed in the data listings.

3.6.4 Screening failure

Screening failures are patients who have been screened and have failed the inclusion and exclusion criteria; these patients are never randomized. Patients who are randomized but never

receive study treatment are not considered as screening failures but will be included in the full analysis set.

3.7 Last contact date

The last contact date will be used for censoring of subjects in the analysis of overall survival.

The last contact date is defined as the latest complete date from the below list on or before the data cut-off date (Table 3-1). The cut-off date will not be used for last contact date, unless the subject was seen or contacted on that date. No date post cut-off date will be used.

Completely imputed dates (e.g. the analysis cut-off date programmatically imputed to replace the missing end date of a dose record) will not be used to derive the last contact date. Partial date imputation is allowed for event (death)/censoring only if coming from the ‘Survival’ eCRF.

The last contact date will be derived for subjects not known to have died at the analysis cut-off using the last complete date among the following:

Table 3-1 Last contact date data sources

Source data	Conditions
Date of Randomization	No condition
Last date subject was known to be alive from Survival Follow-up page	Subject status is reported to be alive or unknown
Start/End dates from further antineoplastic therapy Start/End* dates from drug administration record	Non-missing medication/procedure term Non-missing dose
Response assessment date	Response marked as ‘done’
Laboratory/PK collection dates	Sample collection marked as ‘done’
Vital signs date	At least one non-missing parameter value
ECOG performance status date	Non-missing performance status
Start/End dates of AE	Non-missing verbatim term

3.8 Analysis sets

3.8.1 Full Analysis Set (FAS)

The Full Analysis Set (FAS) comprises all patients to whom study drug has been assigned by randomization. According to the intent to treat principle, patients will be analyzed according to the treatment and stratum they have been assigned to during the randomization procedure.

3.8.2 Safety set (SS)

The Safety Set (SS) includes all patients who received at least one dose of study treatment starting at day 1 and being randomized with at least one dose of Midostaurin or placebo. Patients

will be analyzed according to the study treatment received, where treatment received is defined as the randomized treatment if the patient took at least one dose of that treatment. Patients who started therapy at day 1 but discontinued prior to randomization at day 8 will be listed separately.

3.8.3 Pharmacokinetic analysis set

Pharmacokinetic Analysis Set for all (PAS-all)

The Pharmacokinetic analysis set for all (PAS-all) includes all subjects in the safety set, and provide at least one evaluable PK concentration.

For a concentration to be evaluable:

- Dosing information must be properly documented (data and time of administration)
- The planned dose of midostaurin must be taken prior to sampling.
- For pre-dose samples: no vomiting within 4 hours after the midostaurin dose prior to sampling, the sample is collected before the next dose administration.
- For post-dose samples: no vomiting within 4 hours after midostaurin dosing

The PAS-all will be the primary population used for all pharmacokinetic analyses using trough concentration data.

Pharmacokinetic Analysis Set for full PK profile (PAS-full)

The Pharmacokinetic analysis set for full PK profiles (PAS-full) includes all subjects in the PAS-all, who provide an evaluable PK profile. A profile is considered evaluable if all of the following conditions are satisfied:

- Subject receives the planned first dose of midostaurin on C1D8 of Induction therapy
- Subject did not vomit within 4 hours of the first dose of midostaurin on C1D8 of Induction therapy
- Subject provides at least one primary PK parameter (C_{max}, AUC_{0-t})

The PAS-full will be the primary population used for all pharmacokinetic analyses based on full PK profile data.

3.8.4 Stratum information used for analyses

For all stratified analyses based on the FAS, stratification information will be used as provided by the IRT.

Subgroup analyses by age will use the actual stratum information as derived from baseline characteristics which might be different from that used for randomization as provided by the IRT. In case no baseline characteristics for stratification factors are available, the information as provided by IRT will be used.

3.8.5 Subgroup of interest

The main efficacy endpoints EFS, OS, DFS, CIR, CID, CR/CRi and MRD as well as other key safety endpoints will be summarized by the following subgroups not only to examine the

treatment effect across demographic, baseline disease characteristics variables and anthracyclin for AML induction therapy but also to evaluate midostaurin in these different subgroups:

- Age (< 60 years / \geq 60 years)
- Sex (male / female)
- European Leukemia Network (ELN) 2017 risk classification (favorable / Intermediate / Adverse).
- ITD or TKD signal ratios (<0.015, 0.015 - < 0.03, \geq 0.03-0.05)
- Anthracyclin for AML induction therapy (Idarubicin vs. Daunorubicin).
- Following geographic regions as defined by the World Health Organization (WHO) (<http://apps.who.int/ghodata/>). Hong Kong and Taiwan are not members of the WHO and will be assigned to the region Western Pacific.
 - Region 1: Europe
 - Region 2: Western Pacific
 - Region 3: Americas

Other endpoints and subgroups may be added if deemed necessary. For each of subgroups, The HR and their 95% CIs be presented by means of forest plots for EFS, OS, DFS, CIR and CID.

4 Patient disposition, demographics and other baseline characteristics

The Full Analysis Set (FAS) will be used for all baseline and demographic summaries. Summaries will be reported by treatment group and for all patients. No inferential statistics will be provided.

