This statistical analysis plan (SAP) describes all planned analyses for the clinical study report (CSR) of study CPKC412E2301: a phase III, randomized, double-blind clinical trial of chemotherapy with daunorubicin or idarubicin and cytarabine for induction and intermediate dose cytarabine for consolidation plus midostaurin (PKC412) or placebo in newly diagnosed patients with FLT3-MN (SR<0.05) AML (FLT3 mutant to wild type signal ratio below the 0.05 clinical cut-off).

The content of this SAP is based on protocol CPKC412E2301 amendment 1. All decisions regarding final analysis, have been made prior to final database lock but after unblinding of the study data.

The first interim analysis of the primary endpoint (Event Free Survival (EFS)) for futility has been performed and the study was stopped due to lack of efficacy on 23-Sep-2019 based on DMC recommendation. Subsequently, investigators were notified on the futility outcome and study was unblinded not only for Novartis but also the investigators. While majority of patients discontinued from the study within subsequent weeks, some patients decided to continue protocol planned study treatment. This SAP now describes the analyses for the final CSR which will be generated when all patients discontinued study treatment.

The originally planned efficacy and safety analyses are reduced based on the futility outcome. However, some subgroup analyses have been added (e.g. safety and efficacy by anthracyclin for AML induction therapy (Daunorubicin vs Idarubicin)) and some analyses are only performed now for the final CSR (e.g. QoL, PK, [REDACTED]).

2 Study design, objectives and endpoints

[figure not shown]
This is a randomized, double-blind, multi-center, placebo-controlled phase III study using a group sequential design with two interim analyses for the primary endpoint event-free survival (EFS) and regular safety looks. The study population comprises 502 adult patients with newly diagnosed FLT3-MN (SR<0.05) AML. Patients will be stratified according to age (<60 vs. ≥ 60 years) and will be randomized in a 1:1 ratio into one of two treatment arms:

- Midostaurin + chemotherapy

Or

- Placebo + chemotherapy

Figure 2-1 Study design

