7.2 Statistical hypothesis, model, and method of analysis

The study is designed to test the following statistical hypothesis for EFS using a stratified log-rank test (stratified according to randomization stratification factor of age (<60 vs. \geq 60 years)) at the one-sided 2.5% level of significance:

$$H_{01}: \theta_1 \geq 1 \text{ vs. } H_{a1}: \theta_1 < 1$$

Where θ_1 is the hazard ratio (Midostaurin treatment arm vs. placebo arm) of EFS.

In accordance with the stratified randomization scheme used in the study, a stratified two-sided 3-look group sequential log-rank test with a cumulative type I error rate of $\alpha=0.025$, one-sided, will be used to test the null hypothesis (H_{01}). The stratification factor is:

- Age : <60 vs. \geq 60 years

For EFS, the hazard ratio for treatment effect will be estimated and its two-sided 95% confidence intervals will be reported. The estimation will be based on a cox proportional hazards model with treatment and the stratification factor in it.

In addition, survivorship functions will be estimated by using the Kaplan-Meier product-limit method and displayed as graphs. The estimations are performed by treatment group. Median EFS time and its two-sided 95% confidence intervals will be reported for both treatments.

The primary analysis will be based on the FAS. Response status will be based on investigator's assessments as per the International Working Group (IWG) criteria for AML [[Cheson et al 2003](#), [ELN 2017](#)].

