HRs and 2-sided 95% CIs will be provided based on the stratified Cox proportional hazards model. This model will use the BY statement to derive estimates by subgroup. Point estimates of HR and 2-sided 95% CI will be provided by subgroup in a forest plot.

8 Analysis of the key secondary objective: overall survival (OS)

The key secondary objective is to determine if the addition of midostaurin to standard induction and consolidation therapy, followed by single agent post-consolidation therapy improves overall survival (OS) in patients with newly diagnosed FLT3-MN AML.

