9.13.2 Second EFS interim analysis

Since the study was stopped at first interim analysis, no further analyses were performed.

10 Sample size calculation

The assumption of median EFS of 12.0 months for the control treatment arm for sample size calculations is based on available data for patients with FLT-MN (Bacher et al 2008). It is expected that treatment with test treatment arm will result in a 37.5% reduction in the hazard rate (corresponding to an increase in median EFS from 12.0 months to 17.8 months under the exponential model assumption).

If the true hazard ratio is 0.675, a total of 285 EFS events are required to have 90% power at an one-sided overall 2.5% level of significance to reject the null hypothesis ($HR \geq 1$) using a log-rank test and a 2-look group sequential design with Haybittle-Peto boundary to determine efficacy boundary and gamma spending function ($\gamma = -1.2$) to determine the non-binding futility boundary. Considering a recruitment period of approximately 20 months assuming an increasing recruitment rate to reach 30 patients / month in month 6, 502 patients will need to be randomized to the two treatment arms in a 1:1 ratio. Assuming about approximately 10% patients will be lost to follow-up for EFS, a total of 502 patients will need to be randomized. Given the above assumptions, it is estimated that the 285th EFS event will be observed at approximately 40 months from the date of first patient randomized in the study. The sample size calculation was conducted with software package [East 6.4].

11 Change to protocol specified analyses

No change from protocol specified analysis was made. [REDACTED]

12 Appendices

Please refer to original SAP.

13 Reference

[Allison PD (2000)] Survival analysis Using the SAS system. Cary, NC, SAS Institute Inc.

[Brookmeyer R. and Crowley J. (1982)] A Confidence Interval for the Median Survival Time, *Biometrics* 38, 29-41

[Collet D (1994)] Modelling survival data in medical research. London, Chapman & Hall

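### The SAP's 75 subgroup hazard ratios come with no estimate of whether the effect differs between levels, and a subgroup added after unblinding is not marked as such

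*SAP*

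**What the plan says.** SAP Section 3.8.5 names six factors: age (2 levels), sex (2), ELN 2017 risk (3), ITD/TKD signal ratio (3), induction anthracycline (2) and region (3). It asks for hazard ratios with 95% CIs in forest plots for EFS, OS, DFS, CIR and CID, and it allows more endpoints and subgroups to be added. It gives two purposes. One is to examine the treatment effect across these variables; the other is "but also to evaluate midostaurin in these different subgroups".

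For EFS (Section 7.2.1) and OS (Section 8.2) the method is a stratified Cox model, and "This model will use the BY statement to derive estimates by subgroup". Sections 8.3.3 to 8.3.5 state no subgroup model for DFS, CIR or CID. No section specifies an interaction term.

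SAP Section 1 says decisions on the final analysis were taken "prior to final database lock but after unblinding of the study data". It also says that "some subgroup analyses have been added", and its example is safety and efficacy by anthracycline. SAP Section 11 says "No change from protocol specified analysis was made"; a redaction follows at once. SAP Sections 7, 8.2 and 8.3 make the efficacy results descriptive.

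The protocol had already named age and gender (Section 10.4.3) and age and ELN risk group (Section 10.5). Both lists are open-ended.

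**The concern.** Whether an effect varies across a factor is a question about the difference between levels. A hazard ratio fitted within one level does not answer it, and neither do two CIs side by side, one of which excludes 1. The plan states the across-levels purpose but specifies no quantity that measures it.

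Once the overall comparison has failed, the natural use of these plots is to look for a group in which the drug worked. With 75 intervals, some can be expected to exclude 1 by chance. A reader who relies on Sections 3.8.5 and 11 would not learn that the anthracycline factor was introduced when treatment codes were known.

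That factor is also loosely defined. Under protocol Section 6.1.1.1 an anthracycline is given on Days 1-3 of Induction 1, and again in Induction 2 to patients under 60 who need it. Randomization is on Day 8 (protocol Section 6.5.2). A patient given different drugs in the two cycles has no single level, and the second choice comes after randomization.

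**Working it through.** **1. The plan's own figure.** SAP Section 10: "If the true hazard ratio is 0.675, a total of 285 EFS events are required to have 90% power". Allocation is 1:1 and the test is "at the one-sided 2.5% level of significance". With (1.960 + 1.282)² = 10.51:
- Freedman: 10.51 × (1.675/0.325)² gives 280 events, within 3% of 285. Schoenfeld: 4 × 10.51/(ln 0.675)² gives 273.
- Simulating the sequential design (114, 214 and 285 events; futility HR 0.97; p<0.0001 at the second look) gives power 90.1%, type I error 2.4% and null futility probability 56.5%. The protocol reports 90%, 2.4% and 55.8%.

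The design reproduces. The documents state no subgroup error rate.

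**2. Count.** 2+2+3+3+2+3 = 15 levels; 15 × 5 endpoints = 75 hazard ratios. Under no effect, 75 × 0.05 = 3.75 CIs are expected to exclude 1, half of them (1.875) wholly below 1.

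**3. Upper reference.** If the intervals were independent, the chance of at least one wholly below 1 would be 1 − 0.975^15 = 0.32 for one endpoint and 1 − 0.975^75 = 0.85 for all five. They are not independent: the same patients recur in every factor, and the endpoints overlap.

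**4. The stop.** SAP Section 9.13.1 puts the interim at 145 EFS events with an adjusted futility bound of HR 0.91. Z = −ln(0.91) × √145/2 = 0.568, so a true HR of 1 gives HR ≥ 0.91 with probability 0.71. The observed HR is not stated; from the futility stop it is taken to be 0.91 or more.

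**5. Patient-level simulation, HR 1 everywhere.** Induction failure, relapse and death; six partitions of the same patients; log-rank stratified by age; 3,000 trials per row. Z < −1.96 stands in for a CI wholly below 1. Sample sizes, subgroup sizes, event rates and follow-up are assumptions. The last four columns are chances of at least one such CI.

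| N | Subgroup sizes | Induction failure | Mean EFS events | Any of 75 | Any of 75, given HR ≥ 0.91 | EFS plot | EFS plot, given HR ≥ 0.91 |
|---|---|---|---|---|---|---|---|
| 300 | balanced | 35% | 169 | 0.53 | 0.38 | 0.24 | 0.07 |
| 400 | balanced | 30% | 219 | 0.51 | 0.38 | 0.23 | 0.08 |
| 400 | skewed | 30% | 219 | 0.51 | 0.38 | 0.25 | 0.12 |
| 502 | balanced | 30% | 275 | 0.49 | 0.38 | 0.22 | 0.09 |
| 502 | balanced | 15% | 235 | 0.48 | 0.35 | 0.22 | 0.09 |
| 502 | skewed | 20% | 251 | 0.49 | 0.37 | 0.23 | 0.11 |

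**6. Sensitivity to endpoint correlation.** Normal-score model, 400 patients, 200 events per endpoint, 8,000 trials per row:

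| Pairwise correlation | Any of 75 | Given final HR ≥ 0.91 | Given interim HR ≥ 0.91 (145 of 200 events) |
|---|---|---|---|
| 0.30 | 0.61 | 0.52 | 0.53 |
| 0.50 | 0.56 | 0.43 | 0.45 |
| 0.70 | 0.48 | 0.33 | 0.36 |
| 0.85 | 0.40 | 0.23 | 0.26 |

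For the EFS plot alone this model gives 0.21-0.22 unconditionally and 0.09-0.11 given the interim stop. If the true HR is 1.1, the chance over all 75 given the stop falls to 0.13-0.30.

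**7. Precision of an interaction estimate.** For two equal levels with d events in all, Var(ln ratio) = 2 × 4/(d/2) = 16/d. At d = 145 the SE is √0.110 = 0.332, and exp(1.96 × 0.332) = 1.9. The 95% CI runs about 1.9-fold either way, and wider for small levels.

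**The case against.** The best defence is that the SAP withdraws inference. Sections 7, 8.2 and 8.3 provide no p-values for efficacy and no subgroup claim is planned. Looking at consistency across factors, which Section 3.8.5 does mention, is the ordinary job of a forest plot. This stands as far as it goes: there is no formal type I error to control. But a 95% CI that excludes 1 carries the same nominal message as a p-value, Section 3.8.5 also says the plots are to evaluate the drug within subgroups, and being descriptive does not supply the missing heterogeneity estimate.

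Three further points stand in part.
- Section 1 does disclose that subgroups were added and names anthracycline. The gap is in Sections 3.8.5 and 11.
- Text after the visible sentence of Section 11 is blacked out, so its full content is unknown. The visible sentence is still unqualified and does not fit Section 1, which reports analyses both reduced and added.
- The documents describe no switching between anthracyclines, so the number of patients affected is unknown and may be small.

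It may also be said that interaction estimates only add intervals: 1+1+2+2+1+2 = 9 ratios per endpoint, 45 in all, of which 45 × 0.05 = 2.25 would exclude 1 by chance. That is true, and a reason to label them exploratory. They nevertheless answer the question the plan poses.

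**Conclusion.** The point holds as a reporting and analysis gap. The plan gives 75 level-specific hazard ratios, no interaction estimate, no stated subgroup model for 45 of them (DFS, CIR and CID), and no mark on a factor added after unblinding.

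Under no effect anywhere, the chance that at least one CI lies wholly below 1 is about 40-60% unconditionally. Given a stop with EFS HR ≥ 0.91 it is about one in three, with a range of roughly 23-53%. For the EFS plot alone, given the stop, it is 7-12%. These figures rest on assumed subgroup sizes, event rates and endpoint correlations, and on final data close to the interim data. Even the low figures exceed the 2.5% that applies to a single CI.

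A reader might infer more than the documents support:
- *That a chance benefit after the stop is as likely as not.* That matches the unconditional null. Given the stop, it needs weakly correlated endpoints (about 0.3).
- *That all 75 models use a BY statement.* It is written only for EFS and OS.
- *That several factors were picked with results in hand.* Only anthracycline is shown to be late. Age, sex and ELN risk are in the protocol. The timing of signal ratio and region cannot be determined, because the first SAP version is not available.

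**What to change.** For each factor and each of the five endpoints, fit one age-stratified Cox model with treatment, subgroup and treatment-by-subgroup terms. Print the ratio of hazard ratios with its 95% CI beside the level-specific hazard ratios. For the age factor the strata largely absorb the main effect, but the interaction is still estimable. This also gives DFS, CIR and CID a stated subgroup model.

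Label every plot exploratory and state that one level's CI is not evidence of benefit in that level. Mark subgroups added after unblinding (at least anthracycline) as post hoc in the plots, and list them in Section 11 so that it agrees with Section 1. State whether signal ratio and region were in the first SAP version. Define the anthracycline subgroup by the drug given in Induction 1, which precedes randomization.

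The cost is SAP wording and 6 × 5 = 30 model runs on data already held. The downside is imprecision: about 1.9-fold either way at 145 events with an even split, and wider for small levels. Readers should see that imprecision, because it shows how little the subgroup data can say.

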4.1 Baseline demographics

All demographic data will be summarized by treatment group.

4.2 Disease characteristics of acute myeloid leukemia (AML)

Summary statistics and frequency counts with percentages will be tabulated for diagnosis and characteristics of AML. This analysis will include the following:

- Time since initial diagnosis to start of treatment.
- AML diagnosis, WHO classification 2016.
- Classification of AML
- Bone marrow blast count.
- Presence of Auer rods.
- Platelets, neutrophils, blasts and hemoglobin values in peripheral blood.
- Extramedullary disease assessment.
- European Leukemia Network (ELN) 2017 risk classification will be assigned based on cytogenetic abnormalities and mutations for these patients who are all FLT3 negative. In order to be assigned as intermediate or adverse risk group, patients must have

cytogenetic abnormalities and mutations assessed, however, they can be assigned as favorable when only the respective cytogenetic abnormality or mutation was assessed:

- **favorable risk group** includes any patient with any of the following cytogenetic abnormalities or mutations:
 - t(8;21)(q22;q22.1); *RUNX1-RUNX1T1*
 - inv(16)(p13.1q22) or t(16;16)(p13.1;q22); *CBFB-MYH11*
 - Biallelic mutated *CEBPA*
 - Mutated *NPM1*
- if patients are not in the favorable risk group as defined above, then they are assigned to **adverse risk group** if they have any of the following cytogenetic abnormalities or mutations:
 - t(6;9)(p23;q34.1); *DEK-NUP214*
 - t(v;11q23.3); *KMT2A rearranged*
 - t(9;22)(q34.1;q11.2); *BCR-ABL1*
 - inv(3)(q21.3q26.2) or t(3;3)(q21.3;q26.2); *GATA2, MECOM(EV11)*
 - -5 or del(5q); -7 ; -17/abn(17p)
 - Complex karyotype
 - Mutated *RUNX1* (unless t(9;11) (p21.3;q23.3))
 - Mutated *ASXL1* (unless t(9;11) (p21.3;q23.3))
 - Mutated *TP53*
- if patients are neither in the favorable nor adverse risk group as defined above, they are in the **intermediate risk group** if there is presence of either of the following:
 - Wild type *NPM1*
 - t(9;11)(p21.3;q23.3); *MLLT3-KMT2A*
 - Any cytogenetic abnormalities not classified as favorable or adverse

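### SAP 4.2 tests adverse before intermediate without exempting t(9;11) on the KMT2A line, so t(9;11) patients it lists as intermediate are classed adverse

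*SAP*

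**What the plan says.** SAP section 4.2 gives the only algorithm for ELN 2017 risk in either document. It has three ordered steps.

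1. The favorable group "includes any patient with any of the following cytogenetic abnormalities or mutations", followed by four entries.
2. The adverse group comes next: "if patients are not in the favorable risk group as defined above, then they are assigned to" adverse on any one listed item. One item is "t(v;11q23.3); *KMT2A rearranged", with no exception. Two later items do exempt t(9;11): "Mutated *RUNX1* (unless t(9;11) (p21.3;q23.3") and "Mutated *ASXL1* (unless t(9;11) (p21.3;q23.3").
3. The intermediate group is reached only "if patients are neither in the favorable nor adverse risk group as defined above". One of its entries is "t(9;11)(p21.3;q23.3); *MLLT3-KMT2A".

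The section also requires both cytogenetics and mutations to have been assessed before a patient can be called intermediate or adverse. Favorable can be assigned on the single relevant finding.

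SAP section 3.8.5 then uses "European Leukemia Network (ELN) 2017 risk classification (favorable / Intermediate / Adverse") as a subgroup variable for EFS, OS, DFS, CIR, CID, CR/CRi, MRD and key safety endpoints. Forest plots of hazard ratios are planned for the five time-to-event endpoints. Protocol section 10.5 names ELN risk group as a subgroup but gives no algorithm. Protocol section 1.1 describes the ELN groups only in outline, does not mention 11q23.3 rearrangements, and refers to the published guideline for the full list.

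**The concern.** The same abnormality meets an entry in two groups, and the order of the steps decides between them. Because adverse is tested first and its KMT2A line is unqualified, a t(9;11) patient is stopped there and never reaches the intermediate entry written for that patient. The exemptions on the RUNX1 and ASXL1 lines show that the authors meant t(9;11) to keep a patient out of adverse in those cases. The unqualified KMT2A line defeats them.

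The effect is on two of the three ELN subgroups at once, since each patient moved is added to adverse and taken from intermediate. This SAP governs the final CSR, and its Introduction says that decisions on the final analysis were made after unblinding. That is a reason to have a written rule that leaves the programmer no choice.

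**Working it through.** The plan states no figure on this point, so there is none to reproduce. The check applies the SAP 4.2 rule to a t(9;11) patient.

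**Inputs, all from SAP 4.2**
- Favorable entries: 4.
- Adverse lines other than KMT2A: 8, namely t(6;9); t(9;22); inv(3)/t(3;3); the -5/del(5q), -7, -17/abn(17p) line; complex karyotype; RUNX1; ASXL1; TP53.
- Order: favorable, adverse, intermediate.

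**Does t(9;11) match the KMT2A line?** The intermediate entry places the breakpoint at 11q23.3 and names the fusion MLLT3-KMT2A. The adverse line asks for an 11q23.3 translocation with KMT2A rearranged. It matches, with v = 9, unless v is defined to exclude it. Neither document defines v.

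**Rule as written, t(9;11) present, both assessments done**
- All marker combinations: 2^(4+8) = 4,096.
- No favorable marker: 2^8 = 256. All 256 are adverse through the KMT2A line; 0 are intermediate.
- At least one favorable marker: 4,096 − 256 = 3,840, all favorable.

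So the t(9;11) intermediate entry can never be what classifies a patient. The two exemptions also change nothing, because a patient who qualifies for them is already adverse on the KMT2A line.

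**Rule with t(9;11) exempted on the KMT2A line**
- Without a favorable marker, the patient is intermediate only if the six adverse lines that carry no exemption (8 − 2) are all absent. RUNX1 and ASXL1 may each be present or absent: 2^2 = 4 combinations.
- The other 256 − 4 = 252 stay adverse on another item.
- The 3,840 favorable combinations do not change.

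| t(9;11) with | As written | KMT2A line exempted |
|---|---|---|
| nothing else listed | adverse | intermediate |
| RUNX1 | adverse | intermediate |
| ASXL1 | adverse | intermediate |
| RUNX1 and ASXL1 | adverse | intermediate |
| TP53 | adverse | adverse |
| complex karyotype | adverse | adverse |
| mutated NPM1 | favorable | favorable |
| incomplete assessment, no favorable marker | not assigned | not assigned |

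These are counts of marker combinations, not of patients. They show which profiles change class, not how many patients have them.

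**The case against.** The best defence is that the intent is plain. The section says it assigns the ELN 2017 classification, names t(9;11) separately under intermediate, and exempts it twice in the adverse list. A programmer could take v to mean any partner other than the one named elsewhere, which would remove the conflict. The derivation code is not in the documents, so no patient is shown to have been placed in the wrong group. This stands as a limit: the fault shown is in the written rule, not in a result. It does not rescue the text, because the SAP does not define v that way and wrote the exemption out on the two lines where it wanted one.

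A reader might infer that every t(9;11) patient is misclassified. The documents do not support that. Patients with a favorable marker are favorable under either reading. Patients without complete assessment and without a favorable marker receive no class. Patients with TP53, complex karyotype or another unexempted item are adverse for a separate reason.

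A reader might also infer a sizeable distortion of the adverse subgroup. That would need the frequency of t(9;11) and the size of the adverse group, and the documents give neither. The 502 patients are the planned number; the trial stopped for futility at the first interim analysis, and the SAP gives no actual randomized count.

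Nor does the point reach the main results. SAP sections 7, 8.2 and 8.3 provide no p-values for EFS, no testing of OS and no p-values for the other secondary efficacy endpoints. The stratified analyses use age alone. ELN risk is one of six descriptive subgroup variables.

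**Conclusion.** The point holds in a limited form. As written, SAP 4.2 contradicts itself for fully assessed t(9;11)(p21.3;q23.3) MLLT3-KMT2A patients with no favorable marker and no adverse item other than RUNX1 or ASXL1. It lists t(9;11) as intermediate, yet its order of testing makes these patients adverse. This is an error in the stated rule and not merely missing detail, because the rule followed exactly gives the result that its own entries rule out.

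The consequence is minor. It touches the baseline ELN table and the ELN subgroup summaries and forest plots, all descriptive. The EFS and OS analyses and the futility decision, which rested on EFS, do not depend on it. The number of patients affected cannot be computed from the documents.

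The conclusion assumes that v carries its literal meaning of any partner, since neither document restricts it.

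**What to change.** On the KMT2A line of the adverse list in SAP 4.2, add the exemption for t(9;11)(p21.3;q23.3) already used on the RUNX1 and ASXL1 lines. Stating there that v excludes t(9;11)(p21.3;q23.3) would do equally well. Leave the other adverse items unchanged, and confirm in one sentence that a t(9;11) patient with one of them, such as TP53 or complex karyotype, remains adverse.

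Do not test t(9;11) ahead of the whole adverse list. That would make intermediate the 252 combinations that carry another adverse item with no exemption, a precedence rule that the SAP does not state.

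The cost is one clause of text and one condition in the derivation code, with no new data. The baseline table and ELN subgroup outputs need re-running only if the code followed the literal wording.
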